#### **4. CHANGES IN THE PLANNED ANALYSIS OF THE STUDY**

The population label for Treated Set (TS) is updated to be Safety Analysis set (SAF) based on current project definition. Thus the TS-RT for re-induction treatment becomes SAF-RT, and TS-MT for maintenance treatments becomes SAF-MT.

## **5. ENDPOINTS**

For handling of missing data and the occurrence of inter-current events, unless otherwise specified, see [section 6.6](#).

Baseline for safety data, unless otherwise specified, is the last value prior to initiation of the re-induction treatment (for the re-induction period), or the maintenance treatment (for the pre-flare treatment period and post-flare treatment period), or the disease flare treatment (for the disease flare treatment period).

For the summary of all efficacy data, only those observations which were collected during the on-treatment period (i.e. first dose of spesolimab through to the last dose of spesolimab + 16 weeks) will be used.

Regarding the analyses of the change from baseline by visit for continuous efficacy endpoints, the baseline in current study is used, which refers to the last value prior to initiation of

- the re-induction therapy (i.e. baseline of re-induction period, denoted as R-baseline, corresponding to the week 12 assessment on the prior induction trial),
- or the maintenance therapy (i.e. baseline of the maintenance trial part, denoted as M-baseline, corresponding to the week 12 assessment on the prior induction/re-induction trial part).

For the specification of baseline definition for derivation of the applicable binary MCS endpoints, i.e. clinical response:

- the baseline is defined as the last non-missing value reported prior to the first dose of study drug on the preceding induction study, i.e., the definition of efficacy baseline from the parent trial.

However, for binary MCS endpoints after a disease flare treatment (specifically for disease flare treatment period), the baseline is defined as the last value prior to initiation of each disease flare treatment (i.e. baseline of disease flare treatment period, refers to data from flare confirmation visit with endoscopy or regular maintenance visit with endoscopy before administration of each disease flare treatment, denote as Fx-baseline, 'x' represents disease flare occurrence).

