## **Post-Flare Treatment Period**

The analysis phase as described below is applicable to safety analyses only of the post-flare treatment period.

For the post-flare treatment period of the maintenance period, the analysis phases described below consider the inclusion of data from the following study parts: disease flare treatment with 1200 mg spesolimab single i.v. infusion followed by intensified maintenance dosing with 600 mg s.c. spesolimab q6w, up to the (extended) REP from the last dose of spesolimab (either injection or infusion).

Table 6.1: 3 Flow chart of analysis phases for the post-flare treatment period

Study analysis phase	Description	Start (included)	End (included)
Post-flare treatment phase & Residual effects period	Post-flare treatment period (REP extended)	Date/time of infusion of first flare study drug (Day 1)	Date of end of (infusion or injection) of last administered spesolimab + 112 days at 23:59
Follow-up  phase	Off-treatment period (REP extended)	Date of end of (infusion or injection) of last administered spesolimab + 113 days at 12:00 a.m.	Latest of: i) Date of End-of-Study visit; ii) last contact date on End of Study page at 23:59

Dates are defined individually per patient. If more than one date is associated with a specific visit, measurements associated with a specific date are assigned to a study analysis phase according to the rules specified in the table. An analysis phase will not extend beyond the start date of the following phase.

 The off-treatment period (i.e. Follow-up phase) only exists if the trial completion date is after the date of end of last infusion or injection + 112 days.

The post-flare treatment period only applies to those patients who are administered a disease flare treatment with spesolimab. Assessments done on the same day as the first disease flare treatment dose will be assigned to a study analysis phase based on assessment via date and time. If time is not collected for a particular assessment, then assignment will be to the previous study analysis phase, i.e. to the pre-flare treatment period.

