## **6.7            BASELINE, TIME WINDOWS AND CALCULATED VISITS**

For patients who are included directly into the maintenance period, measurements reported with date and time, and taken prior to start of administration of trial treatment are considered to be pre-treatment values. Measurements reported with a date only (and no time) and taken on the day of first administration of trial treatment are handled in a similar manner, i.e.

assigned as pre-treatment values. These pre-treatment values will be assigned to visits according to the nominal visit number as recorded on the eCRF or as provided by the laboratory.

For patients who are included directly into the re-induction period, measurements reported with date and time, and taken prior to start of administration of trial treatment are considered to be pre-treatment values. Measurements reported with a date only (and no time) and taken on the day of first administration of trial treatment are handled in a similar manner, i.e. assigned as pre-treatment values.

Baseline for derivation of the binary MCS efficacy endpoints, as well as for the efficacy endpoint displays over time are defined in [Section 5](#).

For safety endpoints, baseline for different treatment periods are defined in [Section 5](#).

Measurements taken after start of administration of trial treatment will be considered either on- or off-treatment values based on the definition in [Section 6.1](#), and will be assigned to visits for statistical analysis, if applicable, as defined below.

Analysis of AE data, concomitant medication or non-drug therapies, as well as use of rescue medication will not be based on visits. Therefore, no assignment to time windows will be necessary.

For derivation of the last value on treatment, minimum value on treatment, and maximum value on treatment, all on-treatment values (whether or not selected in any time window; see [Table 6.1: 1](#) and [Table 6.1: 4](#) for definition of the on-treatment period) will be considered; these will be derived for analysis of laboratory and vital signs data. For identification of potentially clinically significant abnormal laboratory values, all values (whether or not selected in any time window) within the on-treatment period will be considered.

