## **7.8 SAFETY ANALYSIS**

All safety analyses will be performed based on each of the SAF-MT and SAF-RT following BI standards. No hypothesis testing is planned.

The analyses based on SAF-MT will be done for the pre-flare treatment period (as defined in [Table 6.1: 2](#)), as well as for the overall maintenance treatment period (as defined in [Table 6.1: 4](#)). The analyses based on SAF-FT will be done for the post flare treatment period (as defined in [Table 6.1: 3](#)), as well as for the disease flare treatment period (as defined in [Table 6.1: 5](#)). For additional analysis on the individual flare safety data based on the SAF-FT, all standard

safety tables will be provided for each flare occurrence using the analysis phases as defined in [Table 6.1: 5](#).

In addition, a subgroup analysis on the overall maintenance treatment period by the number of flare treatments (without flare treatment, with only one flare treatment, with two or more flare treatments as defined in [Section 6.4](#)) will be provided for the following tables based on SAF-MT. Additional subgroup analysis (e.g., by pre-flare regimen) will be considered if necessary.

- Overview on TEAE
- TEAE by SOC, preferred term

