### **7.8.2      Laboratory data**

The analyses of laboratory data will be descriptive in nature and will be based on BI standards ([5](#)). Note that data from the central Laboratory will be used for all displays described below, unless otherwise specified.

For continuous safety laboratory parameters, normalized values will be derived. Normalisation means transformation to a standard unit and to a standard reference range. The process of normalisation, handling of repeat values at the same visit for by-visit displays, as well as standard analyses for safety laboratory data are described in the BI guidance for the Display and Analysis of Laboratory Data ([5](#)). All analyses considering multiple times of the ULN (as described below) will be based on standardized and not normalized values. For continuous safety laboratory parameters, differences to baseline will be calculated.

Only patients with at least one available post-baseline value will be included in the analysis of an individual laboratory parameter. All individual laboratory data will be listed. Values outside the reference range will be flagged.

Descriptive statistics of laboratory values over time and for the difference from baseline (see [Section 6.7](#)) will be based upon normalized values and provided by visit, including the last value on treatment, the minimum value on treatment and maximum value on treatment.

Laboratory values will be compared to their reference ranges; shift tables will be provided for the number of patients with a specific RCTC grade at baseline versus the grade at the last measurement on treatment, as well as the worst grade on treatment. These analyses will be based on standardized laboratory values.

Potentially clinically significant abnormalities will be identified based on BI standard rules which are based on normalized converted lab values, i.e. using SI units. These rules will be listed in the SDL appendix of the CTR. Frequency tables will summarize the number of patients with potentially clinically significant abnormalities. Patients having an abnormal lab value at baseline will be presented separately. A separate listing will present potentially clinically significant abnormal lab values; for each functional lab group all patients' lab values will be listed, if there exists at least one lab value with clinically significant abnormality within the group.

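### The post-flare safety baseline in the SAP predates the flare infusion, so persisting pre-infusion laboratory abnormalities show as shifts in both the pre-flare and the post-flare tables

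*SAP*

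**What the plan says.** SAP Section 5 pairs each analysis period with a safety baseline. The relevant part reads "or the maintenance treatment (for the pre-flare treatment period and post-flare treatment period), or the disease flare treatment", the last item being for the disease flare treatment period. Pre-flare and post-flare share one baseline; the disease flare period has its own. Section 6.7 does not change this: "For safety endpoints, baseline for different treatment periods are defined in" Section 5.

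Table 6.1: 3 starts the post-flare period at "Date/time of infusion of first flare study drug (Day 1"). Table 6.1: 5 starts the disease flare period at the same kind of infusion and ends it 98 days later.

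Section 7.8 states: "The analyses based on SAF-FT will be done for the post flare treatment period", and for the disease flare period as well. Table 6.3: 1 lists laboratory data and vital signs for both. Section 7.8.2 specifies the laboratory displays: "shift tables will be provided for the number of patients with a specific RCTC grade at baseline versus the grade at the last measurement", plus the worst on-treatment grade, change from baseline by visit, and PCSA frequencies, for which "Patients having an abnormal lab value at baseline will be presented separately". Section 7.8.3 gives vital signs descriptive summaries and change from baseline only.

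**The concern.** The 'Post-Flare IV/SC' tables describe patients after the flare infusion and the intensified s.c. schedule. A reader will take a baseline-to-on-treatment shift there as something that happened on that regimen. With a baseline fixed before maintenance, the shift also includes whatever happened during pre-flare maintenance and had not resolved.

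The patients concerned are selected for such change. Protocol Table 2.1:1 defines a flare by higher rectal bleeding, partial Mayo and endoscopic scores, while haemoglobin and CRP are in the routine safety panel (protocol Table 5.2.3: 2). Some laboratory movement before the infusion is therefore plausible. What is at stake is attribution in a long-term safety trial whose interim results are meant to feed investigator brochure updates and submissions (SAP Section 3).

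**Working it through.** No figure in the plan depends on this rule, so there is none to reproduce. The check is a trace of the rule, one worked patient, the timing, and an illustration of size.

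**1. Baseline against period start** (SAP Sections 5 and 6.1)

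| Period | Starts at | Safety baseline: last value before |
|---|---|---|
| Re-induction | first re-induction infusion | re-induction |
| Pre-flare | first maintenance injection | maintenance |
| Disease flare | flare infusion | flare treatment |
| Post-flare | first flare infusion | maintenance |
| Overall maintenance | first maintenance injection | not named |

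Post-flare is the only period whose stated baseline is not taken at its own start. Its AE clock does restart at the first flare infusion (Section 7.8.1).

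**2. One patient.** RCTC grade 0 before maintenance, grade 2 just before the infusion, grade 2 six weeks after it, and never worse.

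- 'Pre-Flare SC': 0 to 2.
- 'Post-Flare IV/SC': 0 to 2 again.
- Disease flare table: 2 to 2.

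The separate presentation of patients abnormal at baseline does not catch this case, because the value was normal at the baseline that applies.

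**3. Timing.** Week 336 is day 2353, and the residual effect period adds 112 days: 2353 + 112 = 2465. For a flare infusion on maintenance day t in a patient treated to week 336, the baseline is t − 1 days old and the post-flare period lasts at most 2465 − t + 1 days.

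| t | Baseline age (days) | Longest post-flare period (days) | 98 days as a share |
|---|---|---|---|
| 85 | 84 | 2381 | 4.1% |
| 169 | 168 | 2297 | 4.3% |
| 337 | 336 | 2129 | 4.6% |
| 673 | 672 | 1793 | 5.5% |

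For a patient who stays to the end, the display with a pre-infusion baseline covers about 4–6% of post-flare time. The share is larger for patients who stop early.

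**4. Size, illustration only.** Among flare-treated patients normal before maintenance, let q be the share who become abnormal before the infusion and are still abnormal after it, and p the share of the rest with a new abnormality after it. Neither is in the documents.

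- Shift against the pre-maintenance baseline: q + (1 − q)p
- Shift against a pre-infusion baseline: (1 − q)p
- Carried-over share: q / [q + (1 − q)p]

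| q | p | SAP baseline | Pre-infusion baseline | Carried-over share |
|---|---|---|---|---|
| 0 | 10% | 10.0% | 10.0% | 0% |
| 5% | 10% | 14.5% | 9.5% | 34% |
| 10% | 10% | 19.0% | 9.0% | 53% |
| 20% | 10% | 28.0% | 8.0% | 71% |

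Over q and p from 5% to 20%, the carried-over share runs from 0.05/0.24 = 21% to 0.20/0.24 = 83%. In this group the carry-over can only add apparent worsening, whatever the inputs.

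**The case against.** The best defence is that a fixed pre-maintenance baseline is a deliberate and respectable choice under continuous exposure. It shows cumulative change on drug, whereas re-baselining at the flare would turn a 0-to-2 deterioration that began on drug into 2-to-2. That is true of the post-flare table taken alone. But the overall maintenance period exists to show long-term safety regardless of flare, and Table 6.3: 1 lists laboratory data and vital signs for it, so cumulative change has a home. Section 5 merely omits to name that period's safety baseline.

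Second, Section 7.8 already plans standard safety tables for each flare, with a pre-infusion baseline. This stands for the first 98 days, which include early intensified dosing. A reader might infer that no display referenced to the infusion exists; that is wrong. The gap is what comes after day 98.

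Third, the benefit of re-baselining depends on sampling. The content of Flow Chart 3 is not in the available text, so a laboratory sample at flare confirmation or infusion cannot be confirmed; Table 6.7: 3 has a baseline row before the infusion but does not list its assessments. Scheduled maintenance laboratory tests are 12 weeks apart (Flow Chart 1A). If the last sample predates the flare, flare-driven changes would still look new. This limits the gain without removing it.

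Other stronger readings also fail:

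- *Every pre-existing abnormality is reported again.* Those already present before maintenance are not shown as new.
- *AE results are distorted.* AEs are assigned by onset, so AE rates and the primary endpoint do not depend on this baseline.
- *The SAP contradicts itself.* Two labelled periods with two stated baselines answer two questions.
- *At least 13 patients are affected, from more than half of 24.* That figure is from an amendment rationale on relapse or flare under the superseded schedule. The same amendment changed the flare definition, and the rationale does not say how many patients received the infusion.

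**Conclusion.** The point holds in a limited form. As written, the post-flare laboratory tables mix change before the infusion with change after it, and persisting abnormalities from pre-flare maintenance are displayed under both labels. Shift tables, PCSA tables and laboratory change from baseline are affected. Vital signs are affected only through change from baseline, since they have no shift or abnormality table. The disease-flare tables resolve the attribution for 98 days, but not for later intensified maintenance.

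This is misattribution in descriptive safety displays. The mechanism follows from the SAP text alone; the magnitude does not. The 21–83% range rests wholly on assumed q and p, and the effect is nil if q is zero. The timing shares assume treatment to week 336.

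**What to change.** In SAP Section 5, make the last value before the first flare infusion the reference for post-flare laboratory shift, PCSA and change-from-baseline displays and for vital-sign change. In the same sentence, name the maintenance-start baseline for the pre-flare and overall maintenance periods, so that cumulative change remains visible there. Table 6.7: 3 already has a pre-infusion baseline row covering safety laboratory data and vital signs that can be reused.

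If the sponsor prefers to keep the present baseline, the minimum is to add the pre-infusion reference beside it, or a flag for abnormalities already present at the infusion.

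The cost is a sentence in the SAP and one extra baseline flag in the laboratory and vital-sign datasets. If the baseline is replaced rather than supplemented, the post-flare table alone no longer shows cumulative change since maintenance start.

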### **5.1 PRIMARY ENDPOINT(S)**

- Exposure adjusted rate of patients reporting a treatment emergent adverse event (TEAE) up to week 336 of maintenance treatment

Please refer to [section 7.8.1](#) for the description of the calculation of exposure-adjusted adverse event incidence rates.

**5.2           SECONDARY ENDPOINT(S)**

**5.2.1       Key secondary endpoint(s)**

Not applicable. No key secondary endpoints have been specified in the CTP.

**5.2.2       Secondary endpoint(s)**

Proportion of patients with clinical remission (CR) at week 336 of maintenance treatment (as defined in [Table 9.1.1: 1](#))

## **6. GENERAL ANALYSIS DEFINITIONS**

### **6.1 TREATMENTS**

The following treatment options are planned in this study:

- For patients who complete treatment in the previous induction study but who do not have a clinical response at week 12 (EoT):
  - Multiple active doses of intravenous spesolimab 1200 mg q4w are administered for 12 weeks (re-induction); responders at week 12 will subsequently receive subcutaneous spesolimab 300 mg q4w as maintenance treatment for up to 7 years;
- For patients who complete treatment in the previous induction study and who have a clinical response at week 12 (EoT):
  - Subcutaneous spesolimab 300 mg q4w as maintenance treatment for up to 7 years.

Note that patients entered into the trial according to CTP version 4.0 or earlier who initially received subcutaneous spesolimab 300 mg q12w as maintenance treatment will be switched to treatment with spesolimab 300 mg q4w per CTP amendment 5.0.

Patients who experience a disease flare during maintenance treatment (as defined in [Table 9.1.1: 1](#)) will be administered a single intravenous dose of spesolimab 1200 mg followed by an intensified subcutaneous maintenance dosing schedule with 600 mg q6w. Note that patients entered into the trial according to CTP version 4.0 or earlier may have received an intensified subcutaneous maintenance dosing schedule with 300 mg q6w; these patients will be switched to 600 mg q6w per CTP amendment 5.0.

The following study phases are defined:

## **Re-Induction Period**

The analysis phase as described below is applicable to both the efficacy and safety analyses of the re-induction period.

Table 6.1: 1 Flow chart of analysis phases for re-induction period

Study analysis phase	Description	Start (included)	End (included)
Screening phase	Screening	Earliest of (Date of informed consent, first screening procedure)	Date/time of start of infusion of first re-induction study drug minus 1 minute
Re-induction treatment phase & Residual effects period	Re-induction on-treatment period	Date/time of start of infusion of first re-induction study drug (Day 1 for re-induction)	Patient does not participate in maintenance treatment period: Date of end of infusion of last re-induction study drug + 112 days at 11:59 pm; Patient participates in maintenance treatment period: Date/time of injection of first maintenance study drug minus 1 minute
Follow-up  phase	Off-treatment period	Patient does not participate in maintenance treatment period: Date of end of infusion of last re-induction study drug + 113 days at 12:00 a.m.	Latest of: i) Date of EOS visit (Week 24 visit); ii) last contact date on End of Study page at 11:59 p.m.

Dates are defined individually per patient. If more than one date is associated with a specific visit, measurements associated with a specific date are assigned to a study analysis phase according to the rules specified in the table. An analysis phase will not extend beyond the start date of the following phase.

 The off-treatment period (i.e. Follow-up phase) only exists if the trial completion date is after the date of end of last infusion + 112 days, and if patient did not continue into the Maintenance period.

 This part applies only to patients entering maintenance period after completing re-induction period; it is expected to occur within the period defined by REP. Note that for safety data, i.e., AE where date and time are collected, an event which occurs on the same day of first dose in the following maintenance period, but prior to the administration are assigned to, and reported as a part of the re-induction period.

Assessments done on the same day as the first re-induction treatment dose will be assigned to a study analysis phase based on assessment via date and time. If time is not collected for a particular assessment, then assignment will be to the screening phase.

The period between last intake of re-induction study drug and first intake of maintenance study drug will be considered as a part of the re-induction analysis phase irrespective of the duration. For re-induction treated patients who do not subsequently receive maintenance treatment, the REP will be applied for the purpose of defining the duration of the on-treatment period.

